8.1 Objectives

8.1.1 Primary objective

The aim of this non-interventional study is to investigate the incidence of specific adverse drug reactions associated with the use of recombinant factor XIII (rFXIII) in patients with congenital FXIII A-subunit deficiency, comprising anti-FXIII antibodies, allergic reactions, embolic and thrombotic events and lack of therapeutic effect.

8.1.2 Secondary objectives

- To further explore the overall safety and effectiveness of rFXIII under conditions of routine clinical care in patients with congenital FXIII A-subunit deficiency, including special population (i.e., children, elderly, pregnant and lactating women, and patients with renal insufficiency).
- To assess the use of rFXIII in patients with congenital FXIII A-subunit deficiency, also other than for prophylactic use.
- To better understand the use of rFXIII and practice patterns in the usual care of patients.

8.2 Endpoints

8.2.1 Primary endpoint

Adverse drug reactions in patients with congenital FXIII A-subunit deficiency treated with rFXIII, comprising anti-FXIII antibodies, allergic reactions, embolic and thrombotic events and lack of effect, collected during study period up to 6 years.

8.2.2 Secondary endpoints

- All serious adverse events collected during study period up to 6 years¹
- All medical events of special interest collected during study period up to 6 years¹
- All medication errors and near medication errors collected during study period up to 6 years 1,2
- Use of rFXIII in patients with congenital FXIII A-subunit deficiency also for other uses than for prophylactic treatment collected during study period up to 6 years.
- Annualised bleeding rate during the study period up to 6 years.

¹ The first three secondary endpoints will be presented by all patients as well as by special populations comprising children, elderly, pregnant and lactating women, and patients with renal insufficiency.

² Medication errors and near medication errors is a subset of the medical events of special interest.

Protocol Date: 02 February 2016 Novo Nordisk Version: 2.0

 Study ID: NN1841-3868
 CONFIDENTIAL
 Version: 2.0

 UTN: U1111-1131-1558
 Status: Final

 EU PAS No.: ENCEPP/SDPP/3687
 Page: 22 of 65

9 Research methods

In this document Physician refers to the individual being overall responsible for the conduct of the non-interventional study at a study site, and the responsible for treating the patient with congenital FXIII A-subunit deficiency.

9.1 Study design

9.1.1 Type of study

This is a prospective, single-arm, multi-centre and multinational non-interventional PASS of safety related to treatment with rFXIII in patients with congenital FXIII A-subunit deficiency. No controls or blinding procedures are applied. There will be no dispensing of any study medication as part of this study. All direction for medication usage is solely at the discretion of the Physician in accordance with their usual care.

The non-interventional PASS will be accessible by all EU countries and other selected non-EU countries, where rFXIII is commercially available. The study duration is 6 years. During the conduct of the non-interventional study active follow-up with included sites will take place in order to ensure and maximise patient enrolment and retention and ensure that safety data are being collected and reported.

9.1.2 Rationale for study design

The rationale for choosing this study design is to assess safety related to treatment with rFXIII in a real-life setting in patients with congenital FXIII A-subunit deficiency. The multi-centre design chosen is to ensure sufficient screening pool of patients for the study. The multinational approach is selected to account for possible variations related to ethnic groups.

Observing patients exposed to rFXIII for up to 6 years is considered an appropriate and reasonable time allowing for further expansion of the known safety of rFXIII for the treatment of FXIII CD. Due to the rarity of the disease and very limited available data with regards to rare adverse events, a systematic sample size calculation is not feasible. It is acknowledged that the small target population limits the potential for enrolment and not all of the diagnosed patients have a current need for treatment of their FXIII CD. The availability of patients for enrolment in the study will also be determined by market uptake of rFXIII for prophylactic treatment of patients with FXIII CD.

Based on the World Federation of Haemophilia (WFH) 68 annual report of 2008¹⁰ the number of diagnosed FXIII CD patients in North America is 136 and in Europe it is 213 resulting in a total of 349 patients in countries in which rFXIII will be marketed. Not all of these patients have a current need for treatment of their FXIII CD disease. The market penetration of rFXIII for the treatment of FXIII CD will determine the number of patients eligible for inclusion in this study.

 Study ID: NN1841-3868
 CONFIDENTIAL
 Version: 2.0

 UTN: U1111-1131-1558
 Status: Final

 EU PAS No.: ENCEPP/SDPP/3687
 Page: 23 of 65

9.1.3 Treatment of patients

The treatment regimens will be in accordance with the approved product labelling in the country of residence of the patient, if rFXIII is used for other indications in patients with FXIII CD this information will also be collected. It is recommended that data collection happens in conjunction with otherwise scheduled visits to the clinic. Patients are expected to remain in the study for up to 6 years depending on time of enrolment.

The study medication used is the commercially available rFXIII (Coagulation Factor XIII A-subunit (recombinant)/INN name: catridecacog, 2500 IU (15 mg)). Administration will be according to the approved package insert (for further information see US PI, EU SmPC, or corresponding local prescribing information). The medication will not be supplied by Novo Nordisk. All direction for medication usage is solely at the discretion of the Physicians in accordance with their usual care guided by the provided product information (US PI and EU SmPC, or corresponding local prescribing information).

There will be no dispensing of any study medication as part of this study. No auxiliary dispensing materials or devices apart from those provided with the commercially available rFXIII product are expected to be used.

The decision to initiate treatment with commercially available catridecacog has been made by the patient/parent and the patient's treating physician before and independently from the decision to include the patient in this study.

For the collection of blood samples, tubes will be provided.

9.1.4 Rationale for treatment

Patients with FXIII CD are lacking the coagulation factor XIII and are therefore predisposed to bleeding from multiple locations; the most serious being intracerebral bleeds (see section 7.2). This is the most common cause of death in this patient group. Treatment with FXIII containing products are therefore used for three purposes: Treatment of an on-going bleed, prevention of bleed in relation to a surgical procedure or general prophylaxis. Due to the long half-life of rFXIII once monthly injection will provide prophylaxis in this patient group (for further information see US PI and EU SmPC, or corresponding local prescribing information).

9.1.5 Study Supplies

9.1.5.1 Study product

The study medication is the commercially available rFXIII (Coagulation Factor XIII A-subunit (recombinant)/INN name: catridecacog, 2500 IU (15mg)) supplied as a lyophilized powder in vials. The powder is to be reconstituted with solvent for injection. After reconstitution the solution is 833

Protocol	Date:	02 February 2016	Novo Nordisk
Study ID: NN19/1 2969	Version:	2.0	

 Study ID: NN1841-3868
 CONFIDENTIAL
 Version: Status: Final

 UTN: U1111-1131-1558
 Status: Final

 EU PAS No.: ENCEPP/SDPP/3687
 Page: 24 of 65

IU/ml corresponding to 5mg/ml. Study medication is to be administrated according to approved product information (EU SmPC, US PI or corresponding local prescription information).

Final approved EU SmPC, US PI or corresponding local prescription is attached to the protocol as country specific product information.

The study medication will not be supplied by Novo Nordisk. All patients enrolled in this non-interventional study will receive their medication through usual commercial channels.

9.1.5.2 Packaging and labelling of study product

These will be as available in the market by prescription and purchase/supply as in routine practice and according to local regulations.

9.1.5.3 Auxiliary supply

No other items or special equipment are required.

9.2 Setting

9.2.1 Number of patients to be studied

Countries planned to participate: All countries in EU where rFXIII is marketed and commercially available will be included. Additional countries where rFXIII is marketed and commercially available may be added to the study (preliminary planned to be Canada, Israel, Switzerland and US).

Anticipated number of study sites: approximately 25-45 (all sites in EU countries and selected non-EU sites where rFXIII is marketed and commercially available and patient(s) are planned to be dosed with rFXIII is to be offered participation in the study if sites have the needed qualifications to perform an non-interventional PASS).

Anticipated number of patients to be included at each study site: 1-10.

9.2.2 Inclusion criteria

- 1. Informed consent obtained before any study-related activities. (Study-related activities are any procedure related to recording of data according to the protocol).
- 2. Able and willing to provide signed informed consent (or patient's legally acceptable representative (LAR) consent, if applicable), as required by local ethics committee, governmental or regulatory authorities.
- 3. Congenital FXIII A-subunit deficiency.
- 4. Actual or planned exposure to the rFXIII.

 Study ID: NN1841-3868
 CONFIDENTIAL
 Version:
 2.0

 UTN: U1111-1131-1558
 Status:
 Final

 EU PAS No.: ENCEPP/SDPP/3687
 Page:
 25 of 65

9.2.3 Exclusion criteria

1. Mental incapacity, unwillingness or language barriers precluding adequate understanding or cooperation.

9.2.4 Withdrawal criteria

- 1. The patient may withdraw at will at any time.
- 2. The patient's parent or patient's LAR may withdraw the patient at any time.

If antibodies to rFXIII product are detected, the treatment with rFXIII may be continued, interrupted or discontinued at the discretion of the Physician. It is strongly encouraged that the patients remain in the study and have regular follow-up visits for monitoring of antibodies until the level has diminished to below clinical significance or detection limit.

Interruption of treatment with rFXIII or termination of treatment with rFXIII is not a criterion for withdrawal from this study.

9.2.5 Rationale for selection criteria

The study population are the patients who based on the indication will benefit from rFXIII treatment. The results of this study can be applied to patients with congenital FXIII A-subunit deficiency. The very few inclusion and exclusion criteria will reduce selection bias. As a multicentre, multinational population has been selected the generalizability of the study is evaluated as high.

Study ID: NN1841-3868 Version: CONFIDENTIAL Final UTN: U1111-1131-1558 Status: EU PAS No.: ENCEPP/SDPP/3687 26 of 65 Page:

9.2.6 Flow chart

Table 9-1 Flow chart

Study periods		Assessment visits	End of study visit
Study periods	Visit 1	(visit 2.1, 2.2, 2.3)	(visit 3)
Vinit tour		In conjunction with	
Visit type	Visit 1	regular visit to clinic	
		Visits with	
Visit window/days	Day 0	recommended 1-6 months interval.	
PATIENT RELATED ASSESSMENTS			
Informed consent	X		
In/exclusion criteria	X		
Withdrawal criteria		X	
Demography	X		
Bleeding treatment history/history of bleeding episodes	X		
Pre-defined complications	X		
Medical history/concomitant illness	X		
Details of diagnosis of FXIII deficiency (FXIII activity and anti-FXIII antibodies)	X		
Concomitant medication	X	X	X
Concomitant illness		X	X
Body measurements	X	X^2	X^2
Vital signs	X		X
Participation in registries	X	X	X
SAFETY ASSESSMENTS			
Adverse drug reaction assessment		X	X
Specific adverse drug reaction assessment			
Blood samples for anti-FXIII antibodies ¹	X^4	X^4	X^3
Embolic and thrombotic events		X	X
Lack of therapeutic effect		X	X
Allergic reactions		X	X
Optional blood samples for FXIII activity ¹	X^3	X^3	X^3
Serious adverse event		X	X
Medical event of special interest		X	X
Medication errors and near medication errors		X	X

Protocol	Date:	02 February 2016	Novo Nordisk
		, , ,	1

 Study ID: NN1841-3868
 CONFIDENTIAL
 Version: 2.0

 UTN: U1111-1131-1558
 Status: Final Page: 27 of 65

BLEEDING ASSESSMENTS			
Bleeding episode description		X	X
Bleeding episodes since last visit		X	X
OTHER ASSESSMENTS			
Diary (instruction/evaluation)	X	X	X
 Prophylactic treatment regimes 			
 Bleeding episode description 			
 Prophylactic treatment related to surgery 			
Documentation of pregnancy		X	X

Footer	Description
1	Blood samples to be drawn prior to any planned rFXIII injection
2	Body weight only
3	Performed as part of routine clinical care established by the Physician, or in case of lack of therapeutic effect and tested simultaneously when a blood sample for anti-FXIII antibodies is collected at a visit after Visit 1 for patients consenting to testing.
4	At Visit 1 and at a visit to be conducted 1 year after entry of the patient into the study for patients consenting to testing. Performed where the collection of blood samples for anti-FXIII antibody assessment is possible within the confines of a non-interventional study. May also be collected at any visit as part of routine clinical care established by the Physician, or in case of lack of therapeutic effect.

9.3 Variables

It is the intention of this study to observe routine treatment of the individual patients. Therefore, the assessments are limited to examinations and collection of information needed to characterise the patient population at initiation and at the end of the study. All study visits should be performed according to normal local clinical practice. No additional visits should be conducted due to the participation in this study. The Physician is encouraged to collect blood samples for FXIII activity and anti-FXIII antibody assessment at the visits mentioned below, see section 9.3.1.1, 9.3.1.2 and 9.3.1.3).

Additionally, due to a regulatory request from the FDA, collection of blood samples for anti-FXIII antibody assessment at Visit 1 and at a visit to be conducted 1 year after the patient entry into the study-for patients consenting to testing. These 2 blood samples should be taken in countries where the collection of blood samples for anti-FXIII antibody assessment is possible within the confines of a non-interventional study (see section 9.3.3.2).

What information to be reported?

The following information, collected as part of normal clinical practise should be reported:

- 1. Safety information including (see section 11)
 - a. adverse drug reactions
 - b. serious adverse events
 - c. medical events of special interest including all medication or near medication errors

 Protocol
 Date:
 02 February 2016
 Novo Nordisk

 Study ID: NN1841-3868
 Version:
 2.0

 UTN: U1111-1131-1558
 Status:
 Final

Status: Page:

28 of 65

UTN: U1111-1131-1558 EU PAS No.: ENCEPP/SDPP/3687

d. Pregnancy in female patients or in the partners of male patients.

- 2. Bleeding episodes (haemostatic treatment used, treatment-requiring bleeding episodes and non-treatment requiring bleeding episodes)
- 3. Effect of prophylaxis
- 4. Surgical interventions

This information will be collected as part of the treatment schedule established by the Physician. A patient diary will be provided if it's part of routine practice at the clinic/department to assist data collection for patients on home treatment.

When should the information be reported?

- 1. When clinical suspicion of decreased therapeutic effect emerges
- 2. At occurrence of adverse drug reaction, serious adverse event or medical event of special interest
- 3. At routine visits with recommended one to six months intervals depending on usual practice
- 4. At occurrence of pregnancy
- 5. Follow up at end of study

The use of rFXIII will be in accordance with the approved product label,in addition, if rFXIII is used in patients with FXIII congenital A-subunit deficiency for other indications than prophylactic (e.g., treatment of bleed or surgery) this information should also be collected. Other haemostatic products and treatments used are to be collected in this study.

Details of the data collection process are described in the subsections below. The data collection should only be recorded in the patient's record and the CRF, if available or performed.

If clinical suspicion of lack of therapeutic effect emerges, the Physician is encouraged to draw blood for anti-FXIII antibody analysis and FXIII activity.

9.3.1 Visit procedures

Patients will obtain routine medical care at their respective clinic in accordance with local practices. All study visits should be performed according to normal local clinical practice. No additional visits should be conducted due to the participation in this study.

At each visit a care provider, in cooperation with the patient, should provide information as specified in the below sections, if available. For patients on home treatment the diary should serve as information base when relevant.

Safety information must be collected during each contact (visit or telephone) with the Physician or study site staff. This may be done by posing a simple question such as "have you experienced any problems since the last contact?"

Protocol		Date:	02 February 2016	Novo Nordisk
Study ID: NN1841-3868	CONFIDENTIAL	Version:	2.0	

Final

29 of 65

UTN: U1111-1131-1558
EU PAS No.: ENCEPP/SDPP/3687
Status: Page:

The Physician must keep a patient enrolment log and a log of patients evaluated for but not included in the study throughout the enrolment period. As this is a non-randomised study, the allocation of patient identification is to be accomplished via a global unique number provided by an electronic system.

Patients enrolled in the study will be provided with contact address (es) and telephone number(s) of the Physician site and/or staff. During a patient's participation in the study, all relevant data should be entered in the CRF.

In case a patient is being prematurely withdrawn from the study the Physician will ensure that the procedures for the last visit are undertaken, if possible. The primary reason (adverse drug reaction or other) for discontinuation must be specified in the CRF.

9.3.1.1 Visit 1

Signed informed consent must be obtained before any data recording (including blood sampling) is performed for this non-interventional study.

At Visit 1 a blood sample for anti-FXIII antibodies, should be taken for patients consenting to testing in countries where the collection of blood samples for anti-FXIII antibody assessment is possible within the confines of a non-interventional study.

The following will be recorded and observed, at the Visit1, after having obtained informed consent:

- Check the time, date and signature of informed consent.
- Check of inclusion and exclusion criteria (please refer to section (9.2.2 and 9.2.3).
- Demography (please refer to section 9.3.2.1).
- Bleeding treatment history (including prophylactic treatment) and History of Bleeding episodes (please refer to section 9.3.2.2).
- Prophylactic treatment regimen
- Pre-defined complications (please refer to section 9.3.2.3).
- Medical history/concomitant illnesses (please refer to section 9.3.2.4).
- Details on diagnosis of FXIII CD (please refer to section 9.3.2.5).
- Concomitant medication (please refer to section 9.3.2.6).
- Body measurements (please refer to section 9.3.2.8).
- Vital signs (please refer to section 9.3.2.9).
- Blood sample for anti-FXIII antibodies, if obtained (please refer to section 9.3.3.1 and 9.3.3.2).
- Optional blood sample for FXIII activity, if obtained (please refer to section 9.3.3.2).
- Diary (instruction) (please refer to section 9.3.5.1).
- Participation in registries (please refer to section 9.3.5.3).

02 February 2016 | Novo Nordisk Protocol Date: Study ID: NN1841-3868

CONFIDENTIAL

UTN: U1111-1131-1558 EU PAS No.: ENCEPP/SDPP/3687

Version: 2.0 Status: Final Page: 30 of 65

9.3.1.2 Assessment visits (visit 2.1, 2,2 etc.)

Patients will obtain routine medical care in their respective treatment centre in accordance with practices of the treatment site. Collection of data and assessment of rFXIII exposure may be performed at all clinical visits after the Visit 1. It is recommended that reporting visits occur with 1 to 6 months intervals according to usual practice. Data collection should happen in conjunction with the patient visits to the clinic.

If clinical suspicion of lack of therapeutic effect emerges or if part of scheduled treatment practice as established by the Physician, sampling for FXIII activity and anti-FXIII antibodies can be performed.

At an assessment visit 1 year after entry of the patient into the study a blood sample for anti-FXIII antibodies should be taken for patients consenting to testing, in countries where the collection of blood samples for anti-FXIII antibody assessment is possible within the confines of a noninterventional study.

The following will be observed and recorded at the assessment visits:

- Assessment of treatment of bleeding episodes since last visit
 - Review of each bleeding episode since last visit (please refer to section 9.3.4.1).
 - Assessment of ineffective treatment episodes, if identified (please refer to section 9.3.3.2).
- Prophylactic treatment since last visit (please refer to section 9.3.5.1).
- Prophylactic treatment related to surgery since last visit (please refer to section 9.3.4.2).
- Adverse drug reaction assessment (please refer to section 9.3.3).
- Specific adverse drug reaction assessment (please refer to section 9.3.3.1).
 - Blood sample for anti-FXIII antibodies, if obtained (please refer to section 9.3.3.1 and 9.3.3.2).
 - Allergic reactions (please refer to section 9.3.3.1).
 - Embolic and thrombotic events (please refer to section 9.3.3.1).
 - Lack of therapeutic effect (please refer to section 9.3.3.1).
- Assessments of serious adverse events (please refer to section 9.3.3)
- Medical events of special interest (please refer to section 9.3.3)
- Assessment of medication error.
- Assessment of the use of rFXIII in patients with congenital FXIII A subunit deficiency, other than for prophylactic use.
- Blood sample for FXIII activity, if obtained (please refer to section 9.3.3.2).
- Concomitant medication assessment (please refer to section 9.3.2.6).
- Concomitant illness assessment (please refer to section 9.3.2.7).
- Body measurements (please refer to section 9.3.2.8).

Protocol
Study ID: NN1841-3868
Date: 02 February 2016 Version: 2.0

Status:

Page:

Final

31 of 65

UTN: U1111-1131-1558

EU PAS No.: ENCEPP/SDPP/3687

• Diary (instruction/evaluation), (please refer to section 9.3.5.1).

- Assessments for withdrawal criteria (please refer to section 9.2.4).
- Participation in registries (please refer to section 9.3.5.3)
- Documentation of pregnancy (please refer to section 9.3.5.2).

9.3.1.3 End of study visit (visit 3)

The end of study visit will be performed 6 years after FPFV in the study. The patients' next visit to the clinic will be defined as their end of study visit, provided they have either a minimum of 2 years participation or 24 exposure days (whichever comes first, unless the patient has dropped out).

If the Physician finds it clinically relevant sampling for anti-FXIII antibodies and FXIII activity can be performed, as part of the treatment schedule established by the Physician and when clinical suspicion of lack of therapeutic effect emerges.

The following will be observed at the end of study visit:

- Assessment of treatment of bleeding episodes since last visit:
 - Review of each bleeding episode since last visit (please refer to section 9.3.4.1).
 - Assessment of ineffective treatment episodes, if identified (please refer to section 9.3.3.2).
- Prophylactic treatment regimen (please refer to section 9.3.5.1).
- Prophylactic treatment related to surgery (please refer to section 9.3.4.2).
- Adverse drug reaction assessment (please refer to section 9.3.3).
- Specific adverse drug reaction assessment (please refer to section 9.3.3.1).
- Optional blood sample for anti-FXIII antibodies, if obtained (please refer to 9.3.3.1 section and 9.3.3.2).
- Allergic reactions (please refer to section 9.3.3.1).
- Embolic and thrombotic (please refer to section 9.3.3.1).
- Lack of the rapeutic effect (please refer to section 9.3.3.1).
- Assessments of serious adverse events (please refer to section 9.3.3).
- Medical events of special interest (please refer to section 9.3.3)
- Optional blood sample for FXIII activity, if obtained (please refer to section 9.3.3.2).
- Assessment of medication error.
- Assessment of the use of rFXIII in patients with congenital FXIII A subunit deficiency, other than for prophylactic use.
- Concomitant medication assessment (please refer to section 9.3.2.6).
- Concomitant illness assessment (please refer to section 9.3.2.7).
- Body weight measurement (please refer to section 9.3.2.8).
- Vital signs (please refer to section 9.3.2.9).
- Diary (evaluation), (please refer to section 9.3.5.1).

Protocol Date: 02 February 2016 Novo Nordisk Study ID: NN1841-3868 Version: 2.0

Status:

Page:

Final

32 of 65

Study ID: NN1841-3868 UTN: U1111-1131-1558 EU PAS No.: ENCEPP/SDPP/3687

• Documentation of pregnancy (please refer to section 9.3.5.2).

- Participation in registries (please refer to section 9.3.5.3)
- Reason for early discontinuation; including date (please refer to section 9.2.4).

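### A consenting patient who leaves before the 1-year visit has no scheduled anti-FXIII antibody sample after Visit 1, because that sample is optional in the end-of-study procedures used at withdrawal

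*Protocol*

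**What the plan says.** The flow chart (Protocol 9.2.6, footnote 4) places the scheduled antibody samples as follows: "At Visit 1 and at a visit to be conducted 1 year after entry of the patient into the study", for patients who consent to testing and where a non-interventional study allows it. The visit sections agree. Section 9.3.1.1 says "At Visit 1 a blood sample for anti-FXIII antibodies, should be taken for patients consenting to testing", and 9.3.1.2 says "At an assessment visit 1 year after entry of the patient into the study a blood sample for anti-FXIII antibodies should be taken". Section 9.3 gives the origin of the pair: "due to a regulatory request from the FDA, collection of blood samples for anti-FXIII antibody assessment at Visit 1" and again at 1 year.

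For premature withdrawal, 9.3.1 says "the Physician will ensure that the procedures for the last visit are undertaken, if possible". The end-of-study list in 9.3.1.3 includes the item "Reason for early discontinuation; including date", so it is evidently meant for early leavers too. In that list the antibody item reads "Optional blood sample for anti-FXIII antibodies, if obtained", and the text above it leaves the matter to the Physician's view of its clinical relevance, saying that "sampling for anti-FXIII antibodies and FXIII activity can be performed, as part of the treatment schedule established by the Physician". The Visit 3 antibody cell of the flow chart carries footnote 3 (routine care or lack of effect), not footnote 4.

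Other provisions allow or urge sampling. Section 9.3 encourages it at the visits of 9.3.1.1 to 9.3.1.3. Section 9.3.3.1 asks for antibody analysis when lack of effect is suspected, including FXIII activity below the expected level. Section 9.3.3.2 permits a sample at any visit and strongly encourages one on any sign of lack of effect.

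**The concern.** Anti-FXIII antibodies are the laboratory-based component of the primary endpoint (8.2.1, 9.7.2.1). Section 9.3.3.1 counts both neutralising and non-neutralising antibodies. An antibody that causes no recognised loss of effect will not prompt symptom-driven sampling, so the scheduled second sample is the only planned way to find it.

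The Full Analysis Set (9.7.1) requires one rFXIII administration and no follow-up sample, and the primary summary is the number and percent of patients (9.7.2.1). An early leaver without a follow-up sample can therefore count as antibody-free with no result after Visit 1. The loss is greatest for a patient who enters with planned rather than actual exposure (9.2.2), because the Visit 1 sample then precedes exposure. Patients receiving their first rFXIII in the study are to have a separate presentation of the endpoints (9.7.2.2), so the missing result would weigh most there.

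**Working it through.** The protocol states no antibody rate, dropout rate, power or precision for this endpoint, so there is no figure of its own to reproduce. The main check is to trace the sampling rules.

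**Scheduled samples after Visit 1, by path (consenting patient, permitting country)**

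| Path | Governing text | Scheduled samples after Visit 1 |
|---|---|---|
| Reaches the 1-year visit | 9.3.1.2, footnote 4 | 1 |
| Stops or switches rFXIII but stays in the study | 9.2.4 (stopping is not withdrawal), then 9.3.1.2 | 1 |
| Leaves the study before 1 year | 9.3.1, then 9.3.1.3 and footnote 3 | 0 |

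One link is an inference. Section 9.3.1 speaks of the last visit without naming Visit 3. The early-discontinuation item in the Visit 3 list supports reading it so.

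**Illustration of size.** The inputs are 30 patients, the anticipated minimum (9.5), and an assumed share leaving before 1 year with no optional sample. For simplicity, all 30 are treated as consenting and in permitting countries. Two quantities follow, with n the number who have a follow-up sample:

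- One-sided 95% upper limit for the antibody rate with zero positives: 1 − 0.05^(1/n).
- Expected observed percent if the true incidence is 10% and unsampled patients stay in the denominator: 10% × n/30.

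| Assumed share leaving unsampled | n | Zero-event upper limit | Expected observed percent |
|---|---|---|---|
| 0% | 30 | 1 − 0.05^(1/30) = 9.5% | 10% |
| 5% (1.5 patients, taken as 2) | 28 | 1 − 0.05^(1/28) = 10.1% | 10% × 28/30 = 9.3% |
| 10% (3 patients) | 27 | 1 − 0.05^(1/27) = 10.5% | 10% × 27/30 = 9.0% |
| 20% (6 patients) | 24 | 1 − 0.05^(1/24) = 11.7% | 10% × 24/30 = 8.0% |

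The last column assumes that leavers have the same true incidence as the others and that no positive is found among them. One missed positive patient is 1/30 = 3.3 percentage points.

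**The case against.** The strongest reply is that nothing here is contradictory. The study is non-interventional, adds no visits and samples within routine care. The two fixed samples are an exception made for a regulatory request, so adding another protocol-driven trigger is a preference. It is true that the sections agree on where samples are scheduled, and the point is therefore one of design. The reply does not close the gap, however, because the withdrawal contact is already foreseen and the patient has already agreed to the sample.

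A reader might infer more than the documents support, in three ways.

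- **That sampling favours patients who did well for a year.** This goes too far. A patient with suspected lack of effect is the one most strongly directed to sampling, at any visit, and sampling is also encouraged at the end-of-study visit. What remains is the leaver with no recognised loss of effect and no routine or voluntary sample.
- **That patients who stop or switch rFXIII fall into the same gap.** They do not. Stopping is not a withdrawal criterion (9.2.4), so they keep the 1-year sample. To call that sample unusable because it is taken off drug would need data on antibody persistence, which the protocol does not give. Moving it forward could also miss antibodies that appear later.
- **That a definite number of patients is lost.** No dropout rate is stated. Only consenting patients in permitting countries are due the samples, and some leavers may be sampled voluntarily. For patients already on rFXIII at entry, Visit 1 is itself a sample under exposure.

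**Conclusion.** The point holds for patients who leave the study before the 1-year sample: the protocol schedules no antibody measurement for them after Visit 1. The existing provisions narrow the gap but leave out antibodies without recognised loss of effect. This rests on reading the last visit in 9.3.1 as Visit 3. It also assumes that the patient consented to testing, is in a country that allows it, and has no optional sample.

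The size is unknown. The tabulated range shows a modest loss of precision, and a modest understatement of the rate if unsampled patients stay in the denominator. It is an illustration, not an estimate. The change is a cheap improvement to one component of the primary endpoint in a study of about 30 patients. It does not correct an error in the analysis.

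**What to change.** Amend 9.3.1, 9.3.1.3, 9.3.3.2 and flow chart footnotes 3 and 4. For a patient who consented to testing, in a country that allows it, and whose participation ends before the 1-year sample, take that second sample at the withdrawal visit, provided the visit takes place and consent to sampling still stands. Report the time from Visit 1 and from the last rFXIII dose to the sample. Patients who stop or switch rFXIII but remain in the study keep the 1-year sample, with time since last dose reported.

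While editing, align the condition for the optional end-of-study sample. Section 9.3.1.3 joins routine schedule and suspected lack of effect with *and*, whereas footnote 3 joins them with *or*.

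The cost is small. One sample of about 2 mL (9.3.3.2) is brought forward, with the same kits and central laboratory and no added visit. The downside is that the interval between the two samples will vary between patients and must be shown. Leavers who miss the withdrawal visit or withdraw consent to sampling will remain unsampled, so the gap shrinks but does not disappear.
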